#### Visit 1: initial discussion

Eligible patients will be contacted by a member of the clinical team by telephone and invited to have a discussion about participating in the study. Following the initial discussion about the study with a member of the research team by phone, an information leaflet will be sent out. A minimum of 24 hours will be provided to allow the patient to consider the given information.

#### Visit 2: consent and baseline data

A second appointment will be arranged to obtain consent should the patient wish to participate in the study, which may be undertaken by an appropriately trained

member of the clinical or research team. Patient's original symptom questionnaire and anorectal physiology reports will be obtained to extract baseline data (CCCS, evacuation time and completeness, quality of expulsive force, opening of the anorectal angle, relaxation of the anal canal, as well as squeeze and push pressures). The patient will then complete CCCS, SMIS, and MyMop questionnaires.

#### Visit 3: BTXA injection

The BTXA injection will be scheduled by the radiology department within 12 weeks. The patient and radiologist carrying out the injection will complete a procedurerelated questionnaire after the procedure. Ultrasound and EMG report on each patient will be obtained following the procedure. The patient will be asked to report any adverse events following the BTXA injection as soon as possible by phone or at follow-up.

#### Visit 4: first follow-up

The patient will attend first follow-up 4-6 weeks after the injection and complete the Cleveland Clinic constipation scoring (CCCS) as well as St. Mark's incontinence scoring (SMIS). They also undergo a repeat anorectal physiology tests.

#### Visit 5: second follow-up

The patient will be given the option of telephone, face-to-face, or electronic follow-up at 3 months following the injection and will complete the CCCS and SMIS. They will also be asked if they have experienced any adverse events.

#### Visit 6: final follow-up

This will take place at 6 months following the injection and will be similar to the second follow-up but the patient will also be asked to complete a MYMOP follow-up questionnaire, and to rank their level of satisfaction with the treatment using a satisfaction thermometer.

Visit	Study Stage	Data		Week	Carried out by	Setting
0	Recruitment	N/A		0	Research team	Pelvic Floor MDT
1	Initial discussion	N/A		1-4	Clinical/research team	Phone
2	Consent and baseline data	CCCS SMIS Anorectal physiology MYMOP		5-6	Clinical/research team	Outpatient clinic
3	BTXA injection	Patient questionnaire Physician questionnaire	ting	18	Radiologist	Outpatient Ultrasound
4	First follow-up	CCCS SMIS Anorectal physiology	ts reporting	22-24	Clinical/research team	GI physiology
5	Second follow-up	CCCS SMIS	events	30	Clinical/research team	Outpatient clinic/ phone/ online form
6	Final follow-up	CCCS SMIS MYMOP follow-up Satisfaction thermometer	Adverse	42	Clinical/research team	Outpatient clinic/ phone/ online form

Study intervention (at visit 3):

Botulinum toxin type A injection (BTXA) – The intervention is an injection of 200 units of Botulinum toxin type A in to the puborectalis muscle under ultrasound guidance.

- In the prone position, the puborectalis muscle will be identified below the coccyx using ultrasound.
- After skin preparation using 70% Isopropyl Alcohol Pad, up to 5ml of local anaesthetic (1% lidocaine) an electromyography (EMG) needle will be inserted and the puborectalis muscle stimulated using a current to confirm correct needle position. Figure 3 demonstrates an example EMG trace on a healthy volunteer at rest (a) and under voluntary contraction (b)
- 200 units of BTXA (Botox, Allergan, Ireland) prepared in 2 ml of saline solution and drawn up using a 2ml syringe.
- 1ml (100 units) of BTXA solution is injected through the EMG needle into the puborectalis muscle to each side of the midline, achieving a total of 200 units.
- The needle is withdrawn, and the procedure is complete.

At the end of the procedure, the patient and physician both complete post-procedure questionnaires.

[figure not shown]
At any stage of the study, expected adverse events will be recorded on the patient's eCRF. If no adverse events have been self-reported this will be confirmed with the patient at the end of every follow-up appointment as part of the follow-up procedure. Serious or unexpected adverse events will be recorded and also reported according to research governance framework guidelines (see Section 14).

Patients can withdraw at any point in the study without the requirement to provide a reason. The data collected from the point of consent to the point of withdrawal will be kept for analysis of retention and follow-up rate, as well as incidents of adverse events depending on the stage at withdrawal. Such patients will return to routine care.

					-~~{	Lon				

Figure 3a. EMG of puborectalis demonstrating tonic activity at rest

Figure 3b. EMG of puborectalis demonstrating voluntary contraction

### 10. Assessment and management of risk

Risk to the participants:

- The potential side-effects and expected AE's from Botulinum toxin type A injection are discussed in section 5.3.1 and 6.4.1, respectively. The potential risks to patients associated with the injection and routine NHS investigations are discussed in section 5.3.2 and 5.3.3, respectively. Any side-effects or AE's experienced by the participants will be assessed and treated by the clinical team and reported in accordance with the procedure outline in section 16 of this protocol.
- The questionnaires used in this study, in addition to routine care, are validated symptoms questionnaires (Cleveland Clinic constipation score, St. Marks Incontinence score, and MyMOP), a satisfaction thermometer, and a short post-procedure questionnaire. None of these contain any questions which are expected to cause mental or emotional harm.
- No financial loss for participants is anticipated as they will be compensated for travel expenses of up to £20 for each face-to-face appointment.

Risk to the clinician:

• There is no increased risk of needle stick injuries associated with this procedure in comparison with the current standard technique of BTXA injection (through the anal canal), which carries a higher risk of needle stick injury as it is guided by the administrator's finger and is not under direct vision.

### 11. Statistical considerations

This is a prospective, uncontrolled, open-label, observational study. Descriptive statistics are appropriate to present data. Data analysis on this basis will be supervised by the chief investigator.

#### 11.1Sample size

The sample size of 10 is a convenience sample (achievable in 12 months) and is not based on *a priori* calculations of statistical power. In the event of preprocedure patient withdrawal, further recruitment will take place to achieve a total of 10 patients.

#### 11.2 Method of analysis

Statistical analysis will not use hypothesis testing. Descriptive statistics will be used to summarise technical feasibility and other outcomes, including the proportion of patients who undergo successful BTXA injection where the puborectalis muscle was identified on ultrasound and on EMG before BTXA injection.

Qualitative summary of technical difficulties, patient satisfaction and reported adverse events will also be documented.

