#### 6.3 Primary endpoint

In order to measure technical practicability, the physician delivering the therapy will be asked to complete a physician acceptability questionnaire at the end of each procedure. The questionnaire subjectively measures the physician's opinion of the procedure difficulty, patient's discomfort, whether or not the procedure is considered successful, and any procedure limitations.

Question/Statement	Scoring
1. Patient's body habitus	kgcmBMI
2. Duration of procedure	minutes
3. Puborectalis identified by USS	□ At rest □ Voluntary contraction
4. Puborectalis identified by EMG	□ At rest □ Voluntary contraction
6. Difficulty of procedure	□ Easy □ Moderate □ Difficult
7. Reason for your answer in question 5.	(Free text)
8. Patient was comfortable	□ Strongly agree □ Agree □ Neutral □ Disagree □ Strongly disagree
9. Procedure was completed successfully	□ Strongly agree □ Agree □ Neutral □ Disagree □ Strongly disagree
10. Procedure limitations	(Free text)

Technical practicability will also be measured objectively by the rate of successful identification of the puborectalis:

- Using ultrasound scan at rest and under voluntary contraction
- Using EMG at rest and under voluntary contraction

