#### 14.2Source data

Study Assessment	Source	Data Transfer
Screening and eligibility checklist	Pelvic floor MDT Electronic medical records	eCRF
Informed consent	Copy in site file and patient's notes	None
Patient questionnaires (including bowel symptoms questionnaire, CCCS, SMIS, MYMOP, post-procedure questionnaire, and satisfaction thermometer)	Patient	eCRF
Physician questionnaires	Physician	eCRF
Radiology report	Patient electronic records	eCRF
Anorectal physiology report	Patient electronic records	eCRF

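### Does section 11.2 need a rule for which muscle states, and which patients, make up its feasibility proportion?

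*Combined protocol and SAP*

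**What the plan says.** Section 6.3 sets out an objective part of the primary endpoint, the rate at which the puborectalis is identified. It has two lines: "Using ultrasound scan at rest and under voluntary contraction" and "Using EMG at rest and under voluntary contraction". Each modality is thus assessed in two muscle states, which gives four rates. The physician form in the same section has one item for ultrasound and one, "Puborectalis identified by EMG", for EMG. Each offers a box for rest and a box for voluntary contraction. A later item asks, on a five-point agreement scale, whether the procedure was completed successfully.

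Section 11.2 rules out hypothesis testing and gives, as an example of the descriptive summary, "the proportion of patients who undergo successful BTXA injection where the puborectalis muscle was identified on ultrasound and on EMG before BTXA injection".

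Section 9 (study intervention at visit 3) gives the sequence. First "the puborectalis muscle will be identified below the coccyx using ultrasound"; then "an electromyography (EMG) needle will be inserted and the puborectalis muscle stimulated using a current to confirm correct needle position". Under Visit 3 it adds: "Ultrasound and EMG report on each patient will be obtained following the procedure". The source-data table in section 14.2 lists a "Radiology report" that feeds the eCRF. Section 9 (Recruitment) continues enrolment until 10 patients have had the procedure. Section 11.1 calls this a convenience sample and replaces patients who withdraw before the procedure.

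**The concern.** Technical feasibility is the primary objective, and this is the only feasibility proportion that section 11.2 names. Four features suggest it is not uniquely defined.

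- **Muscle state.** Identification on a modality could mean rest, contraction, either or both.
- **Base.** The clause about identification can be read as part of the numerator, with all patients scanned as the base. It can also be read as restricting the base to identified patients.
- **Sequence.** The EMG needle follows ultrasound identification. A patient not seen on ultrasound might have no EMG attempt, which leaves two possible denominators for the EMG rates.
- **Recording.** The two identification items have no negative option, so an empty box could mean not identified, not attempted or not completed.

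The success item also has no stated cut-point on its five-point scale. If these choices were made after the results were known, in an open-label study, the most favourable version could become the headline.

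**Working it through.** The plan has no figure of its own to reproduce: the 10 patients are a convenience sample and no target rate is given. All identification rates below are assumptions.

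**1. Do the four rates fix the composite?** Suppose each of the four rates is 9/10, so each box has one miss.
- Both states required on each modality: the composite loses every patient with any miss. That is between 1 patient (all misses coincide) and 4 patients (all differ), giving 6 to 9 of 10.
- Either state enough: a patient is lost only if both states fail on the same modality, which can affect 0 to 2 patients, giving 8 to 10 of 10.
- One named state only: 1 or 2 patients are lost, giving 8 or 9 of 10.

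With each rate at 8/10, the same reasoning gives 2 to 8, 6 to 10 and 6 to 8 of 10. The four rates alone therefore do not determine the composite.

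**2. How large is the gap under a simple model?** Let p be the chance that each box is ticked and r the correlation between the two states within a modality, with the modalities independent. Then P(both) = p² + r·p(1−p) and P(either) = 2p − P(both). The composite over two modalities is the square of each.

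| p | r | both states required | either state enough |
|---|---|---|---|
| 0.95 | 0 | 0.9025² = 0.8145 | 0.9975² = 0.9950 |
| 0.90 | 0 | 0.81² = 0.6561 | 0.99² = 0.9801 |
| 0.80 | 0 | 0.64² = 0.4096 | 0.96² = 0.9216 |
| 0.95 | 0.5 | 0.92625² = 0.8579 | 0.97375² = 0.9482 |
| 0.90 | 0.5 | 0.855² = 0.7310 | 0.945² = 0.8930 |
| 0.80 | 0.5 | 0.72² = 0.5184 | 0.88² = 0.7744 |
| any | 1 | p² | p² (no gap) |

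At p = 0.90 the gap falls from 32 percentage points (r = 0) to 16 (r = 0.5) and to none (r = 1). The two states concern one muscle in one session, so positive correlation is the reasonable expectation. The table also models identification only, whereas the quantity in section 11.2 additionally requires a successful injection.

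**3. One assumed set of 10 patients.** Take ultrasound rest 8/10, ultrasound contraction 10/10, EMG rest 7/10 and EMG contraction 9/10. On the success item, 6 answers are strongly agree and 3 are agree.
- Success = agree or better, base 10: 7/10 (exact 95% interval 34.8 to 93.3%) if rest or both states are required; 9/10 (55.5 to 99.7%) if contraction or either state is enough.
- Success = strongly agree only, base 10: 6/10 (26.2 to 87.8%) under every state rule.

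These intervals overlap heavily.

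**4. The base.** Suppose 10 are scanned, 9 are seen on ultrasound and needled, and 8 are identified on EMG and injected. Success is 8/10 = 80% over all scanned, or 8/8 = 100% over those identified. The second figure is close to circular, because in this example the identified patients are exactly those injected. The EMG rate is 8/10 = 80%, or 8/9 = 88.9% over those needled.

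The documents point to the first base. Section 11.2 speaks of a proportion of patients, section 11.1 replaces only withdrawals before the procedure, and section 6.3 has the form completed at the end of each procedure with room to disagree that it succeeded. A patient scanned but not injected fits that description as a failure.

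**The case for a change.** The strongest case for a change is that a descriptive figure still needs a numerator and a denominator, and that a feasibility study exists to count failures. Sections 5.2 and 5.3.2 describe the muscle as easy to find, but from a small number of non-obese or healthy subjects. Section 5.2 says the approach has not been described in adults, and section 7.2 excludes patients only from a BMI of 40. Some failures are therefore plausible, and writing the rule down now would cost a few sentences.

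Part of this stands. The state rule and the cut on the success item are unwritten, and step 1 shows that the four rates alone do not supply the composite.

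The rest is weaker. Section 6.3 already plans the four rates, and section 11.2 offers its proportion as one summary among others, so a reader will see any difference between rest and contraction. With individual records on 10 patients, every version of the composite can be counted. The empty-box problem has a second source in the ultrasound and EMG report. The lack of a separate EMG row in section 14.2, or of that report in the visit table, does not show that the information is lost, since one radiology report may cover both. A rule that replacement covers only patients who withdraw before scanning would largely restate section 11.1.

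**Conclusion.** The gap is real but is one of missing detail, and no change to the plan is needed. Following the plan as written gives no wrong result: no error rate, sample-size figure or stated decision depends on how the proportion is composed. The possible effect is on the label of one descriptive figure, for example 7/10 against 9/10 in the assumed set. It disappears if the two states agree in every patient and nobody fails a step.

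This rests on two expectations. One is that the analyst reports the four rates with their denominators beside the composite and says which state and which success answers were counted. The other is that patients scanned but not identified or not injected are kept in the denominator as failures, which is the plain reading of sections 6.3, 11.1 and 11.2. Both are ordinary reporting practice for a series of 10.

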# 12. Ethics

This study is a non-CTIMP study using BTXA injection, which is an established treatment for dyssynergic defaecation, and will adhere to the Research Governance Framework for Health & Social Care (2005), the World Medical Association Declaration of Helsinki (1996), ICH Good Clinical Practice Guidelines (1996), current applicable local regulatory requirements, and REC conditions of approval.

Patients with dyssynergic defaecation on the waiting list for biofeedback therapy are offered BTXA injection using a novel approach, avoiding the need for general anaesthetic. It is not offered as an alternative to biofeedback and does not preclude patients from receiving biofeedback therapy as per standard treatment, as the aim of the study is not to assess efficacy of this treatment in isolation but to ascertain its acceptability to patients and physician. The additional symptom questionnaire and anorectal physiology tests performed at follow-up will assess the need for further treatment, which may be biofeedback therapy or repeat injection with BTXA, as part of ongoing NHS care.

#### 12.1 Annual Safety Reporting

The CI will complete the Annual Progress Report (APR) to the REC and the sponsor using the HRA template at the end of the study.

### 13. Public Involvement

Prior to the commencement of this study, with Bowel Research UK through the Patient and Research Together (PaRT) initiation, public opinion on patient facing documents (information leaflet and consent) to develop informative and comprehensive patient literature for the study was sought. Public involvement remains the key focus of this study as its primary focus is on patients' opinion on this new treatment modality.

### 14. Data handling and record keeping

#### 14.1Data management

Data will be handled in accordance with the Data Protection Act 2018 and Barts Health NHS Trust Information Governance policy. This study is performed on a single site.

Source data are kept in the original format. Electronic data (clinic letters, radiology and anorectal physiology reports, pregnancy test) are logged directly on the patient's electronic record. Original copies of physical data (questionnaires, case report forms, and consent forms) are kept in the site file, which is stored in a locked cupboard. Electronic case report forms are generated

electronically from the source data using REDCap and can be verified with the original records.

#### 14.2Source data

Study Assessment	Source	Data Transfer
Screening and eligibility checklist	Pelvic floor MDT Electronic medical records	eCRF
Informed consent	Copy in site file and patient's notes	None
Patient questionnaires (including bowel symptoms questionnaire, CCCS, SMIS, MYMOP, post-procedure questionnaire, and satisfaction thermometer)	Patient	eCRF
Physician questionnaires	Physician	eCRF
Radiology report	Patient electronic records	eCRF
Anorectal physiology report	Patient electronic records	eCRF

#### 14.3Confidentiality

Information related to participants will be kept confidential and managed in accordance with the Data Protection Act (2018), the General Data Protection Regulation (GDPR), NHS Caldecott Principles, the UK Policy Framework for Health and Social Care Research, the ICH Good Clinical Practice Guidelines (1996) and the conditions of Research Ethics Committee favourable opinion.

Patient identifiable information to be collected from the participants include:

- Full name
- Date of birth
- Hospital number
- Contact details

These will be used to contact the participants only and will not leave the study site without prior consent. All case report forms will be anonymised, and participants will not be identifiable in any future publications relating to this study.

Study data will be available to qualified members of the research team, auditors, the REC and any regulatory authorities as required by law.

#### 14.4Record Retention and Archiving

The UK Policy Framework for Health and Social Care Research requires that research records are kept for 25 years after the project has completed. This single site study involve Barts Health NHS Trust patients, is undertaken by Barts Health NHS Trust staff. All research documentation (including consent forms and questionnaires) will be archived at the approved repository for long-term storage of local records, the Trust Corporate Records Centre.

### 15. Interventions and tools

#### **15.1Techniques and interventions**

The injection technique is described in section 9 under study intervention (at visit 3). There is no patent on this technique.

#### 15.2Tools

The post-procedure questionnaire is included in section 6.4.2. Other validated questionnaires used in this study includes the Cleveland Clinic constipation score, St. Marks Incontinence score, MyMOP questionnaire, and a satisfaction thermometer.

#### **15.3Medicinal product**

Botulinum toxin type A (Botox, Allergan, Ireland)

- Indication: focal muscular spasm (of the puborectalis in dyssynergic defaecation)
- Licensing status: PL 00426/0119
- Dosing schedule: injection of 200 units once
- Route of administration: intramuscular injection (to puborectalis muscle)
- Source of Medicinal Product: Royal London Hospital pharmacy
- Storage and dispensing: product will be dispensed on the day of the procedure and stored in a refrigerator before use
- Contraindications:
  - o Known hypersensitivity to BTXA, human albumin, sodium chloride
  - Presence of infection at the proposed injection site
- Side-effects:
  - Common or very common: alopecia; asthenia; autonomic dysreflexia; bladder diverticulum; constipation; dizziness; drowsiness; dry eye; dry mouth; dysphagia (most common after injection into sternocleidomastoid muscle and salivary gland); ecchymosis (minimised by applying gentle pressure at injection site immediately after injection); eye discomfort; eye disorders; eye inflammation; fall; fever; gait abnormal; haematuria; headaches; hot flush; increased risk of infection; influenza like illness; insomnia; joint disorders; leukocyturia; malaise; muscle complaints; muscle weakness; musculoskeletal stiffness; nausea; neuromuscular dysfunction; oedema; pain; paresis; sensation abnormal; skin reactions; subcutaneous nodule; urinary disorders; vision disorders
  - Uncommon: anxiety; coordination abnormal; depression; dysphonia; dyspnoea; facial paralysis; memory loss; oral paraesthesia; photosensitivity reaction; postural hypotension; speech impairment; taste altered; vertigo
  - Frequency not known: abdominal pain; angioedema; angle closure glaucoma; appetite decreased; arrhythmia; diarrhoea; hearing impairment; hypersensitivity; myocardial infarction;

myopathy; nerve disorders; respiratory disorders; seizure; syncope; tinnitus; vomiting

- Procedure specific:
  - Temporary incontinence faecal incontinence occurred in 17 cases (6.9%) from three studies and flatus incontinence occurred in 10 cases (4.1%) from two studies. The symptoms were minor and temporary in all studies.
  - Posterior anal fissure reported in two patients (0.8%) from a single study
  - Rectal prolapse reported in a single patient (0.4%) from a single study

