#### 6.4 Secondary endpoint

#### 6.4.1 Safety

Expected adverse event (AE) related to BTXA injection of the puborectalis include:

- Bruising at injection site
- Local skin reaction at injection site
- Pain at injection site
- Infection at injection site
- New or worsening faecal incontinence

Following the injection, any adverse event reported by the patients will be recorded on the adverse event (AE) form on the patient's eCRF using Research Electronic Data Capture (REDCap). This form will record the nature, severity, time of onset of, and treatment required for the AE. Patients are encouraged to self-report any adverse events as soon as possible by telephone. If no adverse events have been self-reported this will be confirmed with the patient at the end of every follow-up appointment as part of the follow-up procedure. In addition, at the time of first follow-up the injection site will be inspected for any signs of bruising, local skin reaction, or infection. At each follow-up, St. Mark's incontinence score will also be measured to allow detection of new or worsening incontinence, which is the main procedure specific risk associated with this procedure.

The severity of any adverse events will be classified according to the Clavien-Dindo classification of surgical complications:

- Grade 1 any deviation from normal post-operative course without need for pharmacological (antiemetics, antipyretics, analgesics, diuretics, and electrolytes are permitted), surgical, endoscopy, or radiological interventions
- Grade 2 requiring pharmacological treatment other than those permitted in 1 (including blood transfusion and total parenteral nutrition)
- Grade 3 requiring surgical, endoscopic, or radiological intervention
  - Grade 3a not under general anaesthetic
  - Grade 3b under general anaesthetic
- Grade 4 life-threatening complication requiring intensive care management
  - Grade 4a single organ dysfunction, including dialysis
  - Grade 4b multi-organ dysfunction
- Grade 5 death

Serious adverse events (SAE) will be recorded as above and will also be reported as described in the safety reporting section (see Section 16).

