#### 6.4.3 Clinical efficacy

Subjectively improvement will be measured using the Cleveland Clinic Constipation Score (CCCS) and Measure Yourself Medical Outcome Profile (MyMop) assessment pre- and post- intervention.

As part of NHS follow-up care, the patients will undergo repeat anorectal physiology studies (anorectal manometry) to assess the need for further treatment. The post-procedure findings will be compared with pre-procedure findings to identify any changes.

This information will be helpful to make an estimate of the sample size and follow-up rate for future studies.

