### 8. Study design

The overall design is of a single-centre, prospective, uncontrolled, open-label observational study. Patients diagnosed with dyssynergic defaecation, using Rome IV criteria, will be identified from weekly pelvic floor MDT and current waiting list for biofeedback therapy and invited to participate. BTXA injection is not offered as an alternative to biofeedback and does not preclude patients from receiving biofeedback therapy as per standard treatment as this is not a study of treatment efficacy.

All participants will undergo BTXA injection within 12 weeks of recruitment.

Data collection:

- Baseline data collection from patient's initial symptoms questionnaire and anorectal physiology report (pre-procedure).
- MYMOP questionnaire (pre-procedure and at final follow-up)
- Patient and physician procedural questionnaire to be completed at the end of the BTXA injection procedure (see Section 5.3 and 5.4).
- Cleveland clinic constipation score and St. Mark's incontinence score to be completed by the patient at each follow-up.
- Anorectal physiology report (post-procedure) for anorectal manometry results at first follow-up.
- Any adverse events reported by the patient will be recorded on an adverse event form (see Section 5.4).

Data analysis:

- Feasibility and efficacy outcomes will be extracted from the questionnaires and reports and recorded onto Research Electronic Data Capture (REDCap).
- Anonymised summary data will be exported to Excel and descriptive statistics (e.g. mean, confidence intervals of effect) used to present data for publication.

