#### 16.1Adverse Events (AEs)

An AE is any untoward medical occurrence in a participant to whom an intervention has been administered, including occurrences which are not necessarily caused by or related to that intervention. An AE can therefore be any unfavourable or unintended sign (including an abnormal laboratory finding), symptom or disease temporally associated with study activities.

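### Worsening constipation is not systematically detected as a safety outcome, although the score that would show it is collected at baseline and every follow-up

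*Combined protocol and SAP*

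**What the plan says.** **Side-effects.** Section 15.3 gives a formulary list for botulinum toxin type A. Its most frequent category contains the run "autonomic dysreflexia; bladder diverticulum; constipation; dizziness; drowsiness". A separate procedure-specific list in the same section names incontinence, anal fissure and rectal prolapse. Constipation is not in it.

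**Safety outcomes.** Section 6.4.1 begins "Expected adverse event (AE) related to BTXA injection of the puborectalis include" and gives five items. The only bowel item is "New or worsening faecal incontinence". It then gives a score a harm-detection purpose: "St. Mark's incontinence score will also be measured to allow detection of new or worsening incontinence". CCCS has no matching sentence.

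**Adverse event capture.** Section 6.4.1 says "any adverse event reported by the patients will be recorded on the adverse event (AE) form", and patients who have reported nothing are asked at the end of each follow-up. Section 16.1 defines events broadly: "An AE can therefore be any unfavourable or unintended sign". The opening paragraph of Section 16 is narrower and limits recording to events connected, or suspected to be connected, with the procedure.

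**CCCS.** Section 8 has "Cleveland clinic constipation score and St. Mark's incontinence score to be completed by the patient at each follow-up", and Section 9 adds a baseline completion at Visit 2. Section 6.4.3 places the score under efficacy: "Subjectively improvement will be measured using the Cleveland Clinic Constipation Score". Section 8 offers a mean and confidence intervals as examples of the descriptive statistics. Section 11.2 rules out hypothesis testing and promises a qualitative summary of reported adverse events. No section defines or counts deterioration on CCCS.

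**The concern.** Safety is a stated secondary objective. In a group enrolled for constipation, one obvious way to be harmed is for the constipation to get worse. By the definition in Section 16.1 that is an adverse event, but the plan relies on someone calling it one. A patient or investigator may easily see it as the underlying disorder, or as an injection that did not work. If so, it may not be offered at the follow-up enquiry. If it is offered but judged unrelated, the opening rule of Section 16 would allow it to go unrecorded.

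The deterioration would still be in the CCCS data, under a heading that looks only for improvement. If those data are summarised as a mean, improvers can outweigh the patients who got worse. The study could then report a favourable pilot effect and no constipation-related harm, and a future trial would be designed on that picture.

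**Working it through.** **1. How the two scores are treated**

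| | SMIS | CCCS |
|---|---|---|
| Completed at Visit 2 | Yes (Section 9) | Yes (Section 9) |
| Completed at 4–6 weeks, 3 months and 6 months | Yes (Section 9) | Yes (Section 9) |
| Stated harm-detection role | Yes (6.4.1) | None |
| Stated study outcome | New or worse incontinence | Improvement (6.4.3) |
| Worsening in the expected-event list of 6.4.1 | Yes | No |

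The schedules are the same. Only the use of the data differs.

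**2. The route by which worse constipation reaches the safety result**

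- The patient mentions it by telephone or at the follow-up enquiry (6.4.1, 9).
- Someone classes it as an adverse event. Section 16.1 permits this whatever the cause.
- Under the opening of Section 16, it is recorded if thought related to the procedure. Sections 6.4.1 and 16.1 do not impose that condition.
- Section 11.2 summarises what was reported. Worsening seen only in the score does not enter.

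**3. Can a mean hide deterioration with n = 10?**

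The plan has no figure to reproduce: 10 is a convenience sample (11.1), and no CCCS standard deviation or worsening threshold is given. The changes below are therefore assumptions. Improvement is counted as positive.

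Formula: mean ± t × SD/√10, with t on 9 degrees of freedom = 2.262.

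*Nine improve by 5, one worsens by 5.*
- Mean = (9×5 − 5)/10 = 4.0
- Sum of squares = 9×1² + 9² = 90, so SD = √(90/9) = 3.16
- Half-width = 2.262 × 3.16/√10 = 2.26
- 95% CI 1.74 to 6.26

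*Eight improve by 5, two worsen by 5.*
- Mean = (8×5 − 2×5)/10 = 3.0
- Sum of squares = 8×2² + 2×8² = 160, so SD = √(160/9) = 4.22
- Half-width = 2.262 × 4.22/√10 = 3.02
- 95% CI −0.02 to 6.02

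Other assumed patterns, by the same formula:

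| Pattern | Mean improvement | 95% CI |
|---|---|---|
| 8 improve by 5, 2 worsen by 3 | 3.4 | 0.99 to 5.81 |
| 9 improve by 3, 1 worsens by 5 | 2.2 | 0.39 to 4.01 |
| 8 improve by 3, 2 worsen by 5 | 1.4 | −1.01 to 3.81 |

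The mean is favourable in all five patterns. The interval lies wholly above zero in three of them.

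**4. What a count would show**

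Exact (Clopper-Pearson) 95% intervals for the number worsened out of 10:

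- 0/10: 0% to 30.8%
- 1/10: 0.3% to 44.5%
- 2/10: 2.5% to 55.6%

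The count is imprecise, but it shows patients whom a mean conceals.

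**The case against.** The plan does have a route for this event. Any patient-reported event is recorded, absence is confirmed at every follow-up, and the definition in Section 16.1 is wide enough to cover worse constipation. A reader might infer that deteriorating patients are bound to be missing from the safety result. The documents do not support that: a patient who says at follow-up that constipation is worse can be recorded. What remains is that detection depends on how the event is labelled, while a score that does not depend on labelling is left unused for safety.

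A reader might also infer from Section 15.3 that constipation is common after this injection. It does not show that. The list is general to the product and includes eye effects and a swallowing effect tied to a neck muscle. The procedure-specific effects, drawn in Section 5.3.1 from 11 studies and 246 subjects, do not include constipation. Section 6.4.1 is confined to puborectalis injection and is not worded as a closed list, so the omission is understandable. This objection stands. The point does not need a high rate, only that the treated symptom could get worse.

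Nor is the mean fixed as the sole summary: Section 8 gives it as an example, so listings and counts are not excluded. Section 12 also says the follow-up questionnaire and physiology tests will assess the need for further treatment, so individual scores will be looked at in care. Both are fair, but neither commits the study to report deterioration.

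Finally, a rise in CCCS is not proof of harm. There is no control group, Section 5.1 describes improvement falling from 77.4% initially to 46% at four months, and biofeedback may run alongside (Section 8). Any count must therefore be described as worsening of any cause.

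**Conclusion.** The point holds as a gap in systematic detection. CCCS is collected on the same schedule as SMIS, but only SMIS has a safety role, and the narrower recording rule in Section 16 makes it easier for worse constipation to go unrecorded.

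The numerical size is illustrative. On the assumed changes, one patient in ten worsening by 5 points sits behind a mean improvement of 4.0 (1.7 to 6.3), and two in ten behind 3.0 (0.0 to 6.0 after rounding). These rest on chosen values because the documents give no CCCS standard deviation, threshold or expected rate of worsening.

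The consequence is moderate. The study is descriptive, its efficacy data are pilot data, and the primary feasibility endpoint is untouched. The change is worth making because it serves a stated objective with data already held.

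**What to change.** In Sections 6.4.1 and 11.2, add wording to this effect:

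- Each patient's CCCS at Visit 2 and at each follow-up will be listed. Visit 2 is the baseline. It needs naming because Section 9 yields two pre-treatment values, one from the original symptom questionnaire and one completed at Visit 2.
- The number of patients whose CCCS is above baseline at each follow-up, with the size of each change, will be reported beside SMIS under safety and described as worsening of any cause. State the direction of the score; this wording assumes that higher means worse, which the protocol does not say.
- The existing adverse event enquiry at each follow-up will ask specifically about worse constipation.

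Two sets of passages also need reconciling: the expected-event list in 6.4.1 with the side-effect list in 15.3, and the relatedness condition at the opening of Section 16 with 6.4.1 and 16.1.

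**Cost.** Wording, one added question, and one table of at most 10 × 4 = 40 scores. No extra visit or questionnaire is needed. The drawback is that, without a control group, the count mixes harm, waning effect and natural fluctuation. The individual listing lets the reader see the size and timing of each change, but cannot separate those causes.
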